5.2.5 Inclusion of Special Populations

Standard inclusion and exclusion criteria have been selected for the inclusion of healthy subjects and subjects with mild (Child-Pugh class A) and moderate (Child-Pugh class B) impaired hepatic function. Women of childbearing potential are excluded from participation in the study.

5.3 Selection of Study Population

Only volunteers meeting all of the inclusion criteria and none of the exclusion criteria may be enrolled into the study. Prior to performing any study assessments not part of the subject's routine medical care, the Investigator will ensure that the subject or the subject's legal representative has provided written informed consent following the procedure described in Section 9.2.

5.3.1 Inclusion Criteria

All subjects:

- 1. Men and women (of nonchildbearing potential), 18 to 75 years (inclusive) of age at Screening
- 2. Body mass index of 18 to 36 kg/m² (inclusive) with a body weight \geq 50 kg at Screening
- 3. Women must be postmenopausal for at least 1 year, as confirmed by follicle stimulating hormone (FSH) assessments performed at Screening, or surgically sterile (ie, documented hysterectomy, documented bilateral salpingectomy, or documented bilateral oophorectomy). Pregnancy assessments will also be performed on female subjects at Screening and at admission to the study center
- 4. A male participant must agree to use a barrier method, and to have their female partners use highly effective, medically acceptable methods of contraception (ie, methods with a failure rate of less than 1 % per year) as detailed in Appendix I of this protocol during participation in

the study and for at least 90 days after the last dose of IMP. Men must refrain from donating sperm during the same period

- 5. Heart rate in the range of 50 to 99 beats per minute after 10 minutes rest in the semi-supine position at Screening
- 6. Negative drug-screening results and a negative alcohol breathalyzer test at Screening and Day -1. For all subjects, a negative cannabinoid (THC) result on drugs of abuse screening is required to participate in the study. If the result is positive, the Principal Investigator may request to repeat the test. For subjects with hepatic impairment, a positive cannabinoid (THC) result on drugs of abuse screening will not be exclusionary (at Screening or Day -1) if the subject uses cannabinoids on medical recommendation. In subjects with hepatic impairment, positive test for drugs used on medical recommendation will be not exclusionary.
- 7. Negative human immunodeficiency virus 1 and 2 antibodies at Screening
- 8. Subject must have given written informed consent before any study-related activities are carried out and must be able to understand the full nature and purpose of the study, including possible risks and adverse effects
- 9. Absence of acute hepatitis.

Subjects with normal hepatic function:

- 10. Healthy volunteers, as judged by the Investigator
- 11. Medical history without any ongoing clinically relevant findings as judged by the Investigator
- 12. Physical examinations without any clinically relevant findings as judged by the Investigator.

Subjects with impaired hepatic function:

- 13. Subjects with mild (Child-Pugh class A) and moderate (Child-Pugh class B) impaired hepatic function at Screening
- 14. Subjects with confirmed cirrhosis (excluding primary biliary liver cirrhosis)
- 15. Systolic blood pressure in the range of 80 to 180 mmHg and diastolic blood pressure in the range of 45 to 95 mmHg at the Screening visit after 10 minutes rest in the semi-supine position
- 16. A 12-lead ECG recording that is normal, or with abnormalities which are not hazardous to the subject in the opinion of the Investigator at Screening.

5.3.2 Exclusion Criteria

All subjects:

- 1. Subject has taken an investigative medication within 30 days prior to administration of IMP
- 2. Subject has donated blood within 60 days or plasma within 14 days prior to Screening
- 3. Subject is lactating
- 4. Diseases or surgeries of the gastrointestinal tract, which could influence the gastrointestinal absorption or motility
- 5. A history of epilepsy
- 6. A history of malignant diseases other than basalioma
- 7. Clinically relevant allergies that require medical treatment, as judged by the Investigator
- 8. Inability to refrain from alcohol intake during confinement. Subjects should not consume more than 14 (women) or 21 (men) units of alcohol a week (unit = 1 glass of wine (125 mL) = 1 measure of spirits = ½ pint of beer)
- 9. Any other clinically relevant disease, which in the Investigator's opinion would exclude the subject from the study
- 10. Inability to communicate or cooperate with the Investigator (eg, language problem, illiterate, poor mental status) or to comply with the requirements of the entire study, including dietary restrictions
- 11. Smoking > 10 cigarettes per day, or equivalent use of other forms of nicotine (ie, patches, gum, chewing tobacco, vaping) for the duration of the study
- 12. Antacid drugs, H2-blocker and proton pump inhibitors might affect the absorption of tepotinib. H2-blocker or proton pump inhibitors should be stopped 5 days prior to Day 1 until Day 2. Antacids should not be taken 1 hour before the IMP administration until 2 hours after the IMP administration.
- 13. Renal dysfunction (defined as creatinine clearance < 60 mL/minute, calculated by use of the Cockcroft-Gault formula)

Healthy Subjects:

- 14. Presence of hepatitis B or hepatitis C or previous infection with hepatitis C, treated with Sofosbuvir or other antiviral compounds
- 15. Use of any medication, including multivitamin preparations, received within 10 days prior Day 1 or 6 times the elimination half-life, whichever is the longest, until the End of Study visit,

except the occasional use of paracetamol/acetaminophen or ibuprofen (not > 500 mg per day) within 7 days before Day 1 until the End of Study visit.

Subjects with impaired hepatic function:

- 16. Primary biliary liver cirrhosis
- 17. Nonstabilized chronic heart failure (New York Heart Association Class III and IV)
- 18. Hepatocarcinoma
- 19. Hepatic encephalopathy Grade III and IV
- 20. Sepsis or spontaneous bacterial peritonitis within the last 2 years prior to Screening
- 21. Gastrointestinal bleeding within 30 days prior to or during Screening
- 22. Esophageal varices > Grade II at Screening
- 23. Acute hepatic failure of any etiology (including viral, toxic, or drug induced)
- 24. Portosystemic shunt
- 25. Current intake of any drug with dose dependent hepatotoxicity, such as paracetamol/acetaminophen (> 500 mg per day)
- 26. Change in used medication (prescribed by a physician or over-the-counter medication) other than for hepatic insufficiency within 7 days prior to Day 1
- 27. Co-medication inducing or inhibiting P-gp, BCRP, OCT1, OCT2, MATE1, or MATE2 should be stopped from 5 days prior to Day 1 until the End of Study visit
- 28. Clinical evidence of severe ascites
- 29. Ascites requiring paracentesis within 21 days prior to Day 1.

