5.2.3 Rationale for Endpoints

The primary and secondary endpoints are relevant exposure parameters that are required to assess the impact of hepatic impairment on the exposure of tepotinib.

The rationale for including metabolites as secondary endpoints are as follows:

M506 was identified as the only major circulating metabolite and contributes with a low extent to the overall activity. Its contribution to safety and tolerability is not evaluated by nonclinical safety, as tepotinib is developed under the ICH S9 guidance.

M506 is formed from MSC2156119J with a median t_{max} of 24 hours, ranging from 24 to 60 hours, and showed an apparent geometric mean half-life of 93 hours, ranging from 66 to 145 hours, estimated on concentration data from 4 subjects. M506 consists of 2 enantiomers, the S-enantiomer, MSC2571107, and the R-enantiomer, MSC2571109, which have been included as secondary endpoints. MSC2571109 represents the major human plasma metabolite of tepotinib (64.6% of parent AUC_{0-240h}), while MSC2571107 is a metabolite of less significance (4.54% of parent AUC_{0-240h}). A bioanalytical assay is available, which analyzes tepotinib and the enantiomers.

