5.2.4 Risks

On the basis of available clinical data, asymptomatic increase of lipase and amylase are considered as an identified risk of tepotinib. Such elevations have been reported for a number of other tyrosine kinase inhibitors with molecular targets other than c-Met (eg, sunitinib, imatinib, sorafenib) and can therefore be regarded as a class effect. The underlying mechanism that causes the enzyme elevation is unknown. The pancreas was not identified as a potential target organ in animal toxicology studies. No pancreatitis has been reported so far.

Tepotinib was identified as a P-glycoprotein (P-gp) substrate, as well as an inhibitor of P-gp, BCRP, OCT1, OCT2, MATE1, and MATE2. Intestinal and systemic drug-drug interactions on the transporter level with relevance cannot be ruled out. In vitro drug transporter interaction studies revealed a pronounced inhibition of OCT1, OCT2, and MATE2 by the major metabolite MSC257119A with the potential for clinically relevant drug-drug interactions considering its current mean exposure at steady state in clinical studies.

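### The protocol names tepotinib as an inhibitor of six transporters, but criterion 27 and Section 6.5.2 stop only inducers and inhibitors of them, so a narrow-therapeutic-range substrate in a hepatic impaired subject meets no directed check before dosing

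*Protocol*

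**What the plan says.** Section 5.2.4 of the Protocol states: "Tepotinib was identified as a P-glycoprotein (P-gp) substrate, as well as an inhibitor of P-gp, BCRP, OCT1, OCT2, MATE1, and MATE2". It continues: "Intestinal and systemic drug-drug interactions on the transporter level with relevance cannot be ruled out". On the metabolite it says: "In vitro drug transporter interaction studies revealed a pronounced inhibition of OCT1, OCT2, and MATE2 by the major metabolite", and it sees potential for clinically relevant interactions "considering its current mean exposure at steady state in clinical studies".

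For hepatic impaired subjects, exclusion criterion 27 (Section 5.3.2) says "Co-medication inducing or inhibiting P-gp, BCRP, OCT1, OCT2, MATE1, or MATE2 should be stopped from 5 days prior to Day 1", and the restriction runs to the End of Study visit. Section 6.5.2 repeats it.

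Section 6.5.1 sets the conditions for permitted medicines. In general, a medicine must be needed for the subject's welfare, must not interfere with the study medication, and is left to the Investigator's discretion. Impaired subjects may also continue prescribed drugs and vitamins taken on a stable regimen. Criterion 26 excludes an impaired subject for "Change in used medication (prescribed by a physician or over-the-counter medication) other than for hepatic insufficiency within 7 days prior to Day 1".

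Healthy subjects are treated differently. Apart from occasional paracetamol or ibuprofen, criterion 15 excludes them for "Use of any medication, including multivitamin preparations, received within 10 days prior Day 1", with a longer washout for drugs of long half-life.

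**The concern.** Section 5.2.4 describes two directions of interaction. As a P-gp substrate, tepotinib can have its own exposure changed by drugs that induce or inhibit P-gp. As an inhibitor of all six transporters, it can raise the exposure of other drugs that those transporters carry. The second direction spans the full six-transporter list, and the drugs at risk in it are substrates.

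Criterion 27 and Section 6.5.2 take over the six-transporter list but apply it to inducers and inhibitors, which is the first direction. The rule as written therefore does not address the risk from which its list comes.

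What is at stake is the safety of impaired subjects, the only group allowed ongoing background therapy. If a subject takes a substrate with a narrow therapeutic range, its level could rise after dosing. The IMP is given once and cannot be taken back, so Screening is the effective point of control.

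**Working it through.** **Is the gap closed elsewhere in the Protocol?**

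| Provision | What it covers | Covers substrates? |
|---|---|---|
| Criterion 9 | Other clinically relevant disease | No |
| Criterion 15 | Nearly all medication, healthy subjects | In effect yes, but healthy subjects only |
| Criterion 25 | Drugs with dose-dependent hepatotoxicity | No |
| Criterion 26 | Recent changes in medication | No |
| Criterion 27 and Section 6.5.2 | Inducers and inhibitors of the six transporters | No |
| Section 6.5.1, non-interference condition | Effect of the co-medication on tepotinib | No, opposite direction |
| Section 6.5.1, welfare and discretion | General Investigator judgement | Not directed at substrates |
| Section 6.5.5 | Management of specific adverse events | No specific measure proposed |

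All six transporters in Section 5.2.4 reappear in criterion 27 and Section 6.5.2. No provision for impaired subjects mentions substrates.

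**How many subjects.** Six Child-Pugh A plus six Child-Pugh B gives 12 in Part 1. Optional Part 2 would add 6, for 18 in all. The Protocol does not say how many would take such a drug.

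**How far the metabolite warning carries over to a single dose.** The Protocol gives no figure to reproduce, so this is an approximation.

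- Input: Section 5.2.3 says M506 "showed an apparent geometric mean half-life of 93 hours, ranging from 66 to 145 hours, estimated on concentration data from 4 subjects".
- Assumptions: linear mono-exponential kinetics; a steady-state reference of 500 mg once daily, for both parts; and the M506 half-life applied to the metabolite named in Section 5.2.4.
- Accumulation: R = 1/(1 − 2^(−24/t½)).
- Single-dose share of steady state: 1/R at 500 mg and 2/R at 1000 mg.

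| t½ (h) | R | 500 mg share | 1000 mg share |
|---|---|---|---|
| 66 | 4.49 | 22.3% | 44.6% |
| 93 | 6.11 | 16.4% | 32.8% |
| 145 | 9.23 | 10.8% | 21.7% |

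A different reference dose moves these figures. Section 3.1 reports daily doses of up to 1000 mg in HCC. Against 1000 mg daily, the central 500 mg share would be 16.4%/2 = 8.2%. For tepotinib itself, the Protocol gives no interaction size from which to calculate.

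**Timing of a remedy.** Criterion 26 covers Day -7 to Day -1, so a medically indicated switch has to be made by Day -8. Screening opens on Day -28, 20 days before that. After discharge on Day 4, impaired subjects have visits on Days 5, 6, 7, 8, 10, 13, 15 and 22, eight in all. Scheduled laboratory tests and ECGs among these fall on Days 8 and 22.

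**The case against.** The strongest reply is that this is a wording asymmetry with little behind it. Each subject receives one dose. The firmest warning in Section 5.2.4 rests on in vitro data and steady-state metabolite exposure; for the parent drug the text only leaves interactions open. No drug is named, and narrow therapeutic range is this review's description of the substrates of most concern, not a category that the Protocol defines. Applying criterion 27 already makes the site check each medicine against the same six transporters. Medication history is taken at Screening and updated at admission, and creatinine clearance must be at least 60 mL/minute. Subjects stay in until Day 4, adverse events and concomitant medication are followed at every visit, and causality assessment considers concomitant drugs. Section 3.1 also refers sites to the Investigator's Brochure, which may advise on substrates.

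Most of this stands, and it limits the weight of the point. It does not close the gap. None of the measures tells the site what to do with a substrate, and a check aimed at inducers and inhibitors lets a pure substrate through. The sentence leaving intestinal and systemic interactions open carries no steady-state qualifier, and Part 2 may double the dose.

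A reader might go further and infer that sites have no guidance on substrates at all. The documents do not show that, because the Investigator's Brochure is not at hand. Nor is the background medication of impaired subjects unconditional: Section 6.5.1 sets welfare, non-interference, discretion and stability as conditions.

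**Conclusion.** The point holds as a modest single-dose safety gap. The inhibition risk stated in Section 5.2.4 has no matching rule for substrates in impaired subjects, 12 in Part 1 and 6 more if Part 2 runs.

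Three stronger readings are not supported:

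- **That harm is to be expected.** The Protocol gives neither an interaction size for tepotinib nor the number of subjects on such drugs, so no harm rate can be stated.
- **That the primary result is compromised.** The gap concerns the effect of tepotinib on other drugs. The AUC and Cmax comparison for tepotinib is unaffected, and the inducer and inhibitor restriction is not in dispute.
- **That the metabolite figures cap the risk.** About 16% (11% to 22%) at 500 mg and about 33% (22% to 45%) at 1000 mg are approximations under the stated assumptions. The half-life comes from 4 subjects, the 500 mg reference is assumed, and impaired subjects may differ. The figures are not an upper bound and say nothing about the parent drug.

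**What to change.** Keep the inducer and inhibitor restriction as it is. Add to criterion 27 and Section 6.5.2:

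*Candidates taking a narrow-therapeutic-range substrate of P-gp, BCRP, OCT1, OCT2, MATE1 or MATE2, identified from the Screening medication history, are not enrolled unless (a) the drug was already stopped or switched on medical grounds more than 7 days before Day 1, or (b) the Investigator documents before dosing that it can be continued safely with clinical review at the scheduled visits. A drug continued under (b) is a permitted medication only if it does not itself induce or inhibit any of the listed transporters.*

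The 7-day limit agrees with criterion 26. The last sentence prevents a drug allowed under (b) from triggering the mandatory withdrawal in Section 6.5.2. It also stops (b) from overriding the existing ban for a drug that is both substrate and inhibitor. Nobody has to give up stable therapy for the study.

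The cost is a medication check at Screening, some candidates not enrolled, and possibly slightly slower recruitment. The rule uses the medication history already taken and the visits already planned, so no new assay or visit is needed.

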5.4 Criteria for Initiation of Study Treatment

Inclusion and exclusion criteria will be checked within the Screening period and at Day -1. Subjects meeting all of the inclusion and none of the exclusion criteria will be enrolled to Part 1 or Part 2 of the study, as appropriate, and admitted to the study center on Day -1 for IMP administration on Day 1.

5.5 Criteria for Subject Withdrawal

5.5.1 Withdrawal from Investigational Medicinal Product Administration

Not applicable since the IMP is administered only once in the study.

5.5.2 Withdrawal from the Study

Subjects may withdraw from the study at any time without giving a reason.

A subject must be withdrawn from the study if any of the following occur during the study:

- Subject withdrew consent
- Participation in another clinical study during the duration of this study
- Use of nonpermitted concomitant medications, as defined in Section 6.5. However, any medications that are considered necessary for the subject's wellbeing may be given at the discretion of the Investigator
- Protocol noncompliance judged as significant by the Investigator, including noncompliance to the required study considerations (eg, food/diet requirements)
- Subject lost to PK sampling
- Any event that unacceptably endangers the safety of the subject.

If there is a medical reason for the withdrawal, the subject will remain under the supervision of the Investigator until satisfactory health has returned or care has been transferred to the subject's general practitioner or to a hospital consultant.

In case of premature withdrawal from the study, the assessments scheduled for the End of Study visit should be performed, if possible, with the focus on the most relevant assessments (see Table 1). Regardless, the appropriate electronic case report form (eCRF) section should be completed.

Subjects who are withdrawn after IMP administration and are not evaluable will be replaced, as discussed by the Investigator and Medical Responsible of the Sponsor.

5.6 Premature Termination of the Study

The clinical study may be terminated prematurely or suspended at the request of the Health Authorities or if new safety or efficacy information leads to an unfavorable risk benefit judgment for the IMP. The Sponsor may discontinue the study if it becomes unjustifiable for medical or ethical reasons, for poor enrollment, or because of discontinuation of clinical development of the IMP or withdrawal of the IMP or comparator from the market for safety reasons.

The Health Authorities and Institutional Review Boards (IRBs) will be informed about the discontinuation of the study in accordance with applicable regulations.

5.7 Definition of End of Study

The end of the study is defined as the completion of the last visit of the last subject.

6 Investigational Medicinal Product and Other Drugs Used in the Study

The term "Investigational Medicinal Product" refers to an active substance or a placebo being tested or used as a reference therapy in a clinical study, including products that have a marketing authorization but are formulated, packaged, or administered differently from the authorized form, used for an unauthorized indication, or used to gain further information about the authorized form.

6.1 Description of the Investigational Medicinal Product

Tablet Formulation 2 (film-coated tablet formulation) of tepotinib will be used in this study. For Part 1, 500 mg tablets of Tablet Formulation 2 will be used. For Part 2, 100 mg tablets of Tablet Formulation 2 or a bioequivalent formulation may also be used for doses other than 500 mg or 1000 mg.

Tepotinib 100 mg and 500 mg film-coated tablets for Phase 1, 2 and 3 clinical studies contain the excipients D-mannitol, silica colloidal anhydrous, crospovidone, magnesium stearate, and Opadry® II pink (for 100 mg) or Opadry II yellow (for 500 mg). The film-coated tablets are intended for oral administration.

6.2 Dosage and Administration

All subjects will receive the IMP once only in the course of the study. A single oral dose of 500 mg in Part 1 and up to 1000 mg in Part 2 tepotinib tablets will be administered to subjects after they have completed a standard breakfast. The IMP administration will occur 30 minutes after the start of the intake of a standard meal. Subjects should eat this meal within 25 minutes or less. The IMP will be administered with 240 mL of water. The subject will remain fasting for 4 hours after the breakfast, after which a standardized lunch will be served. Further details on the standard breakfast are provided in Section 6.5.3.

6.3 Assignment to Treatment Groups

Part 1 will have 1 treatment group and 1 control group receiving a single dose of 500 mg tepotinib. Part 2 is optional, and if conducted, will have 1 treatment group receiving a single dose of between 500 mg up to 1000 mg, as per SMC decision.

6.4 Noninvestigational Medicinal Products to be Used

Not applicable

6.5 Concomitant Medications and Nondrug Therapies/Interventions

All concomitant medications taken by the subject during the study, from the date of signature of informed consent are to be recorded in the appropriate section of the eCRF, noting the name, dose, duration and indication of each drug. Nondrug interventions and any changes to a concomitant medication or other intervention should also be recorded in the eCRF.

